9.4.3. Outcome of AE

The adverse reaction / event outcomes include:

- Recovery
- Not yet recovered

- Recovered but sequelae
- Death
- Loss of visit

9.4.4. Relationship between AE and vaccine

Researchers should make the best interpretation of AE, and assess the possible causal relationship between vaccine inoculation and alternative reasons (such as history of underlying diseases, combined treatment of causation). This applies to all AE, including severe and non-severe.

The assessment of causality will be reasonably explained in the following or more aspects of the event:

- The similar reaction to the solution was observed in the past;
- identical events of similar types solution have been reported in the literature;
- the incident occurred along with the time of the vaccination, and again after the secondary vaccination

According to definitions, all the collected AE (that is, the local adverse event of the collection of the report) will be considered to be related to vaccination.

The causal relationship of AE should be evaluated according to the following questions, and according to your judgment, the reasonable possibility of relationship between AE and vaccination is caused by the vaccination:

- Related: there is a suspicion that a link between vaccine and the AE (do not need to be determined); the vaccine has a reasonable potential for promoting the AE.
- Unrelated: there is no suspicion that a link exists between vaccine and the AE; there are other more likely causes, and vaccination has not been suspected to promote the AE.

9.4.5. Reporting of SAEs

Any serious adverse event, including death due to any cause, which occurs during this study, whether or not related to the investigational products, must be reported immediately. The un-blinding of single cases by investigators in the course of the clinical trial will only be performed if relevant for the safety of the participant.

[figure not shown]
The SAE report form must be filled and submitted to Pharmacy Board of Sierra Leone and the

Sierra Leone Ethics and Scientific Review Committee within 48 hours of the first knowing about the occurrence of the event. All SAEs will be recorded on the case report form and source documents.

In case of death of a participant post-vaccination, and may be correlated with the vaccination, verbal autopsy must be carried out as per WHO Guidelines using “The 2014 WHO verbal autopsy instrument” (Appendix 12, <http://www.who.int/healthinfo/statistics/verbalautopsystandards/en/>). A copy of autopsy report should be attached with the SAE form.

All suspected adverse reactions related to an investigational products, both in unexpected and serious (SUSARs) are expedited reporting to investigator. Also post-study SUSARs that occur after the patient has completed a clinical trial and are reported by an investigator to the sponsor, qualify for expedited reporting.

The sponsor is responsible for the prompt notification to all concerned investigators, the fatal or life-threatening SUSARs will be notified by the sponsor to the Pharmacy Board of Sierra Leone as soon as possible but no later than seven calendar days after the sponsor has first knowledge of the minimum criteria for expedited reporting. All other SUSARs and safety issues deserving expedited reporting must be reported to the competent authority and -dependent on national provisions - to pharmaceutical supervision department in Sierra Leone as soon as possible but no later than 15 calendar days after the sponsor has first knowledge of the minimum criteria for expedited reporting. The SAEs/ SUSARs report procedure should as follows:

Sponsor will also be responsible for reporting the SAEs to the DSMB for safety review. The fatal or

life-threatening SUSARs no later than seven calendar days. Other SUSARs no later than 15 calendar days.

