7.5. Criteria for pausing the study or an early termination

DSMB will review the reported safety data in the participants after vaccination. During the study

period, if an increase of risk for participants is noticed, the DSMB should promptly inform the principal investigator and sponsors. Sponsors, investigators and DSMB will have a panel meeting, and then DSMB will make final decision to pause or call an early termination of the study.

Administration of study injections and new enrollments will be paused, if:

- One serious adverse event may be associated with vaccination, or
- Incidence of new HIV infection post-vaccination reported in one (1) participant during 6 months after vaccination.

The study may come to an early termination, if:

- One fatal serious adverse event definitely associated to vaccination, or
- Incidence of new HIV infection reported in 1% (5 participants) during the 6 months post-vaccination, or
- Required by sponsor, or
- Required by regulatory authority, or

Required by institutional review board (IRB).

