9.7.6. Statistical Considerations for the DSMB

All the SAEs report along with the HIV infection report will be submitted to the DSMB. The DSMB will follow the SAE reports and determine the relationship with the vaccination of the investigational vaccines. If a SAE is considered to be “may be associated with vaccination”, or the reported incidence of new HIV infection is excess 2.5%, then the DSMB may unblind the reported cases, and re-estimate the risk of participants. If necessary, the DSMB discuss with sponsor and investigator about the risk of participants in this study which may resulting in a pause or an early termination of the trial. If a fatal SAE is considered “to be definitely associated with vaccination” or the reported incidence of new HIV infection is excess 5%, then the DSMB shall unblind the reported cases and call an early termination of the trial if necessary.

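### For one possibly related SAE, 7.5 makes a pause mandatory and 9.7.6 makes it discretionary; neither says whether dosing is held while the DSMB decides, and 9.4.5 allows 7 or 15 days to tell the DSMB of a SUSAR

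*Protocol*

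**What the plan says.** **The trigger and its effect in 7.5.** The rule is mandatory: "Administration of study injections and new enrollments will be paused, if" one of two conditions is met, the first being "One serious adverse event may be associated with vaccination, or". The same section says that, after a panel meeting with sponsors and investigators, the "DSMB will make final decision to pause or call an early termination of the study".

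**The same trigger in 9.7.6.** The DSMB is the assessor: "The DSMB will follow the SAE reports and determine the relationship with the vaccination of the investigational vaccines". If it considers that an SAE may be associated with vaccination, "then the DSMB may unblind the reported cases, and re-estimate the risk of participants". If necessary it then discusses with sponsor and investigator the risk of "participants in this study which may resulting in a pause or an early termination of the trial".

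**Who is told, and when (9.4.5).** The SAE form goes to the Pharmacy Board and the ethics committee within 48 hours of first knowledge of the event. SAEs reach the DSMB through the sponsor. The text gives DSMB limits for SUSARs only: seven calendar days if fatal or life-threatening, then "Other SUSARs no later than 15 calendar days". No DSMB limit is given for SAEs that are not SUSARs. A general sentence requires every SAE to be reported immediately but names no recipient.

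**Investigator's role.** Under 9.4.4 researchers assess causality for every AE, and a suspicion is enough to call an event related. No sentence says whether that judgement is what sets off the pause in 7.5.

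**The concern.** A rule that acts on a single event is only as fast as its slowest step. Here the body that judges relatedness and has the final say on a pause can, within the written limits, hear of the event later than the regulator and the ethics committee. The two sections that describe its response also disagree on whether a pause must follow.

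Each participant is dosed at one visit, so a pause protects only those not yet vaccinated. If site staff take 9.7.6 as the operative text and wait for the DSMB, the notification time determines how many more people are injected before the event is reviewed. If they take 7.5 as an instruction to hold dosing on suspicion, it does not. The protocol should settle which applies.

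**Working it through.** The plan states no figure on this point, so there is none to reproduce. The check has two parts.

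**1. Texts side by side for one SAE that may be associated with vaccination**

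| Question | 7.5 | 9.7.6 |
|---|---|---|
| Is a pause required? | Yes (will) | No (may, if necessary) |
| Who judges the association? | Not stated | DSMB |
| Who decides on the pause? | DSMB, after a panel meeting | DSMB discussion with sponsor and investigator |
| Is dosing held meanwhile? | Not stated | Not stated |

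The first row is a direct conflict. The last row is a gap in both sections. Section 7.5 is also unclear within itself, because it states a mandatory pause and makes pausing a DSMB decision.

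**2. What the notification limits could mean in doses**

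*Inputs from the protocol:* 500 participants (7.4); one dosing visit each (9.3.2); 2:1:1 allocation, so three quarters receive active vaccine; limits of 2 days (48 hours) for the regulator and ethics committee, and 7 or 15 days for the DSMB (9.4.5).

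*Assumptions:* even accrual over R = 30, 60 or 90 days, because the timetable in section 11 is marked as for reference only; all limits run from the same starting point; dosing continues until the DSMB is told.

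Doses per day: r = 500/R = 16.67, 8.33 and 5.56.

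Most doses given before the DSMB is told = r × L, where L is the limit in days:

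| R (days) | L = 2 | L = 7 | L = 15 |
|---|---|---|---|
| 30 | 33 | 117 | 250 |
| 60 | 17 | 58 | 125 |
| 90 | 11 | 39 | 83 |

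Excess over a 48-hour notice, for the 7-day and 15-day limits:

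| R (days) | Full limit used: r × (L − 2) | Half the limit used: r × (L/2 − 2) | Mean over a uniform event time, full limit |
|---|---|---|---|
| 30 | 83 and 217 | 25 and 92 | 71 and 155 |
| 60 | 42 and 108 | 13 and 46 | 39 and 93 |
| 90 | 28 and 72 | 8 and 31 | 26 and 65 |

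The last column allows for events late in recruitment, when fewer doses remain. Mean doses are r × (L − L²/(2R)). For R = 30 this gives 16.67 × (2 − 4/60) = 32.2, 16.67 × (7 − 49/60) = 103.1 and 16.67 × (15 − 225/60) = 187.5, so the mean excess is 103.1 − 32.2 = 70.8 (unrounded terms) and 187.5 − 32.2 = 155.3.

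Three quarters of any count are active doses; for example, 0.75 × 250 = 188 and 0.75 × 83.3 = 62.

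**If the site holds dosing on the investigator's suspicion**, dosing stops whatever the DSMB limit is, and the excess is 0.

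**The case against.** - **A SUSAR already presupposes suspicion.** The 7- and 15-day limits apply only when someone before the DSMB suspects the vaccine. Section 9.4.4 sets a low bar for that, and 9.2.2 requires the investigator's causality assessment before any unblinding. That suspicion can itself meet the 7.5 trigger, and 7.5 does not make the pause conditional on the DSMB having been told. The sections can be read together as a hold on suspicion followed by a DSMB decision. This is a sensible reading, and on it the exposure is zero. It stands as a possibility, but no sentence states it.
- **Other safeguards exist.** SAEs must be reported immediately. Under 9.4.1 staff telephone the principal investigator at once (in the paragraph on day 8 onward). The sponsor, the regulator ("Required by regulatory authority, or") and the IRB can each bring about early termination. These reduce the practical risk but do not set a time for the DSMB.
- **The reporting diagram in 9.4.5 is not shown in the available text.** It may give the DSMB a shorter time. That would answer the timing part, though not the conflict between 7.5 and 9.7.6.
- **The limits are maxima and the counts are conditional.** The figure of 250 needs 30-day accrual, at least 15 recruitment days left, the full limit used, a SUSAR neither fatal nor life-threatening, and an investigator, sponsor, regulator and ethics committee who all let dosing go on after being told. This stands in full.

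A reader might infer that the two sections disagree on whether dosing stops at once. They do not go that far: neither gives any timing. A reader might also infer that the plan permits 15 more days of dosing after a suspected reaction. The documents do not support that either, because 7.5 can be read as an immediate hold.

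**Conclusion.** The point holds as a conflict of wording in a stated stopping rule, together with a written DSMB time limit too slow for a rule that acts on one event. The current text supports both without any assumption about accrual, subject to the diagram for the time limit.

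The size depends on which reading the site follows. It is no extra doses if dosing is held on suspicion. If dosing waits for the DSMB, a full 15-day delay spans about 83 to 250 of 500 participants and a 7-day delay about 39 to 117, for accrual over 90 to 30 days. These counts illustrate the stakes; they are not a forecast. They also assume that a possibly related SAE would count as unexpected. That is plausible, since 4.2 reports no SAE in the Chinese Phase I trial and no serious adverse reaction in the African one, but it cannot be confirmed without the Investigator's Brochure.

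This is a cheap safety improvement worth making. It does not question the pause criterion, the sample size or the analysis.

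**What to change.** - **9.4.5:** add the DSMB as a recipient of the 48-hour form for every SAE, and keep the 7- and 15-day limits for regulatory SUSAR reports. If the reporting diagram already gives the DSMB a shorter time, align the sentence with it.
- **7.5:** state that once an SAE is judged possibly related under 9.4.4, the investigator holds injections and enrolment until the DSMB decides.
- **9.7.6:** replace the discretionary pause with a DSMB decision to continue or lift that hold.

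The change is about one sentence in each section and one more recipient for a form already being sent. The downside is slightly more DSMB correspondence and occasional short holds for events later judged unrelated.

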9.4.6. Reporting of the occurrence of new HIV infection or pregnancy

The participants are asked to report new diagnosed HIV infection or pregnancy to the investigator or safety follow-up staffs. The report procedure shall follow the SAE report procedure and using SAE report form. The occurrence of new HIV infection also need to be reported to the DMSB for safety evaluation. Any pregnancy after vaccination during the study period will be monitored/followed up till delivery and 28 days after delivery of a normal baby. If delivery baby with abnormality, the cause of the abnormality will be investigated by the DSMB.

9.4.7. Record of safety observation

Any clinically meaningful adverse event occurred after vaccination should be recorded in the diary card. Verification and medical visits by investigator respond to adverse events are required, such as investigation of medical history, physical examination and necessary laboratory examination (if required). Participants should receive appropriate medical treatment until the adverse event decline completed with complete records.

The record of adverse events should include the following:

- Description of adverse events
- Start and end time of adverse events
- Severity (grade)
- Relationship with vaccination
- Laboratory findings
- Treatment measures
- Outcome

If there are allergies, SAE, or a level 3 adverse events or above happening in safety observation period, medical treatment should be provided until symptoms disappeared or stabilization of symptoms. Record the details of visit exactly.

9.4.8. Medical treatment of AE

If the participants received local or systemic adverse reactions or events or serious adverse events, researchers should provide appropriate treatment or medical consultation to reduce or remove suffering. The medical treatment of green channel could be started if it is necessary. The medical procedures and outcome should be exactly recorded.

9.5. Laboratory assay and immunogenicity assessments

9.5.1. Zaire Ebola virus GP-specific antibody responses

9.5.1.1. Time point

Serum antibody titers against the Zaire Ebola virus GP will be determined at day 0 (immediately before vaccination), day 14, day 28, and day 168 (month 6).

9.5.1.2. Blood sample processing and detection methods

The blood sample shall be isolated for serum, and the isolated serum from each participants shall be collected into several sterile tubes, 1ml in each, and store in cryogenic refrigerator below -20°C .

Zaire type of Ebola virus antibodies will be detected by ELISA.

9.5.1.3. Evaluation

The level of antibody to Zaire glycoprotein after immunization was the primary evaluation measurements of the immunogenicity in serum. The antibody responses in different time points will be compared between vaccine group and placebo group.

9.5.2. Neutralizing antibody titers response to Ad5

9.5.2.1. Time point

Neutralizing antibody titers response to human Ad5 will be detected at day 0, day 14, day 28 and day 168 (month 6).

9.5.2.2. Blood sample processing and detection methods

The isolated serum will be used for the Neutralizing antibody titers response to human Ad5 assays. Laboratory staffs will detect neutralizing antibody in serum by use of replication defective human type 5 adenovirus expressing luciferase (Ad5-luc).

9.5.2.3. Evaluation

The neutralizing antibody titers against human Ad5 pre-vaccination and the post-vaccination will be compared to reveal the difference. The relationship between the pre-existing antibody titers against Ad5 and the specific immune response against Zaire Ebola virus (including both humoral and cellular responses) will be explored.

9.5.3. Detection of HIV

9.5.3.1. Time point

HIV infection will be detected at day 0 and day 168 (month 6). Two drop of finger blood will be collected for each HIV test.

9.5.3.2. Evaluation

Participants with negative response to HIV infection on day 0 could join into the group. The HIV infection incidence of the participants during the study will be compared with the average HIV infection incidence in local area. And the HIV infection incidence in the vaccine group and placebo group will be compared.

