7.4. Sample size

We set the sample size as 250 people in high-dose vaccine group, 125 people in low-dose and placebo group, respectively. The sample size is 500 in total.

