9.7.5. Statistical methods

9.7.5.1. Safety analysis methods

Safety analysis of this experiment is mainly descriptive analysis of incidence rate of adverse reaction

or adverse events. A chi-square test can be used to compare the proportion of participants with adverse reactions in different groups, Fisher's exact test will be used when it is necessary.

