9.7.5.2. Immunogenicity analysis methods

Analysis of immunogenicity indicators on antibody levels need to do logarithmic transformation, the results of analysis should be shown in GMT, standard deviation, median, minimum and maximum values and 95% confidence intervals. ANOVA will be used to compare the GMTs among different groups, and then SNK methods will be used for further pairwise multi-comparison. Chi-square test can be used to compare categorical indicators between groups such as positive conversion rate of immune response, if it is necessary, Fisher's exact test will be used. Statistical analysis method of repeated measures data can be used to analyze experimental data at different time points in this study.

SAS software was used for all analyses, test statistics and the corresponding p values are given. All statistical tests were two-sided and significance was set at $P \leq 0.05$ (more detailed information, please read the reference the statistical analysis plan (SAP)).

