12.3. Potential danger and danger minimization

12.3.1. Benefit and Risk

The subjects/participants in this study will not pay for the Ad5-EBOV vaccines and will obtain the reasonable transportation expenses, lost income, blood donation, and nutrition fee compensation. The subjects will get one vaccination with Ad5-EBOV or placebo. The participants will get the protection of Ad5-EBOV which can protect them from threat of Ebola virus in a period of time. At the same time, there may be some adverse reactions after injection. Common vaccination adverse reactions include: fever, tenderness and swelling on the injection site, redness. The adverse reactions are usually relieved in the 3-5 days after they occur.

It has been reported in other country's clinical study results that adenovirus vector may cause a prolonged clotting time in a period, but will not influence the safety of life generally. Also, adenovirus vector may increase the risk of HIV infection. But as the decrease of the level of neutralizing antibodies against adenovirus vector after vaccination, the risk of HIV infection will also decrease. So subjects will be closely followed to observe the infection rate of HIV for 6 months after vaccination. We will counsel subjects to avoid any behavior that will increase the risk of contracting HIV

In addition, the recent VSV vector vaccine clinical studies have found that vaccination may cause joint pain, which need to be observed in the study.

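### With both doses pooled, the planned vaccine-versus-placebo HIV comparison cannot show an excess in vaccinees at two-sided P≤0.05 with fewer than 12 infections; report it as an interval with an upper limit instead

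*Protocol*

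**What the plan says.** Section 12.3.1 tells the reader that "adenovirus vector may increase the risk of HIV infection", and section 7.2.2.1 makes post-vaccination HIV infection a secondary safety endpoint. Section 9.5.3.2 plans two comparisons. One is external: "The HIV infection incidence of the participants during the study will be compared with the average HIV infection incidence in local area". The other is randomised: "And the HIV infection incidence in the vaccine group and placebo group will be compared". This point concerns only the second.

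For safety, section 9.7.5.1 says "Safety analysis of this experiment is mainly descriptive analysis of incidence rate of adverse reaction" or events, and then: "A chi-square test can be used to compare the proportion of participants with adverse reactions in different groups, Fisher's exact test will be used when" necessary. No other between-group method for a safety outcome is named. Section 9.7.5.2 adds: "All statistical tests were two-sided and significance was set at" P≤0.05. That sentence stands under the immunogenicity methods but is worded to cover every test.

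On size, section 7.4 says: "We set the sample size as 250 people in high-dose vaccine group, 125 people in low-dose and placebo group, respectively". Section 7.5 pauses injections and enrolment at one new HIV infection and lists, among the grounds on which the study may end early, "Incidence of new HIV infection reported in 1% (5 participants) during the 6 months post-vaccination".

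**The concern.** The protocol names a possible vector harm, promises a randomised comparison on it, and offers for that comparison only a significance test at 0.05. Infections will be few and the allocation is three vaccinees to one placebo recipient. Under 3:1 allocation most infections are expected in vaccinees even if the vaccine does nothing, so a run of infections confined to vaccinees is weak evidence to the test. A P value above 0.05 is then very likely whether or not the vaccine raises risk.

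At stake is what the trial can say about HIV when it is used to support a phase III decision. A bare statement of no significant difference would carry almost no information about harm, yet could be carried forward as if it did. An interval from the same data would show how much excess risk remains possible.

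**Working it through.** **Inputs.** High dose 250, low dose 125, placebo 125 (section 7.4), so pooled vaccine 375. Two-sided 0.05 (9.7.5.2). Fisher's exact test (9.7.5.1), since expected counts are small. Follow-up 168 days. Visit loss about 15% (9.7.1). Background HIV incidence is not given, so it is assumed.

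**The plan's own figures.** The protocol states no power or minimum event count for HIV. Its count of five is 1% × 500 = 5. The trial is sized on antibody positivity, 85% v 95% at 2:1. With mean rate (0.85 + 2×0.95)/3 = 0.9167, n(low) = [1.96·√(1.5×0.9167×0.0833) + 0.8416·√(0.85×0.15 + 0.95×0.05/2)]² / 0.10² = 98.2. That gives 99 low dose and 2×98.2 = 196.3, so 197 high dose, as section 9.7.1 states. HIV played no part in the sizing.

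**Smallest significant excess, doses pooled.** Given k infections in all, the chance that x fall in vaccinees is C(375,x)·C(125,k−x)/C(500,k) if there is no effect. The two-sided P value adds the probabilities of all splits no more likely than the one observed.

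- 5 v 0: 0.2357 for the observed split, plus 0.0873 + 0.0142 + 0.0009 for 2, 1 and 0 in vaccinees: p=0.338.
- 11 v 0: 0.0407 + 0.0258 + 0.0059 + 0.0009 + 0.0001: p=0.073.
- 12 v 0: 0.0303 + 0.0108 + 0.0021 + 0.0003: p=0.0435, the first at or below 0.05.
- 12 v 1: p=0.20, so a single placebo infection raises the bar further.

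Uncorrected chi-square agrees: 5 v 0 p=0.19, 11 v 0 p=0.053, 12 v 0 p=0.043. After 15% loss (319 v 106) the minimum is still 12 (Fisher p=0.043).

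**Other comparisons the wording would allow (Fisher).**

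| Comparison | Five, all in vaccinees | First significant excess in vaccinees |
|---|---|---|
| Pooled 375 v 125 | p=0.34 | 12 v 0 (p=0.044) |
| High dose 250 v 125 | p=0.17 | 9 v 0 (p=0.032) |
| Low dose 125 v 125 | p=0.060 | 6 v 0 (p=0.029) |

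In the opposite direction, pooled, three infections all on placebo suffice: C(125,3)/C(500,3) = 0.015.

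**Power to show harm, pooled.** Risk over 168 days is 1 − exp(−rate × 168/365.25). The probabilities of all significant splits with the higher proportion in vaccinees are summed over binomial(375, p1) and binomial(125, p0).

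| Assumed background per 100 person-years | p0 | Doubling | Tripling | Five-fold |
|---|---|---|---|---|
| 0.2 | 0.09% | <0.01% | <0.01% | <0.01% |
| 0.5 | 0.23% | <0.01% | <0.01% | 0.1% |
| 1 | 0.46% | 0.01% | 0.4% | 9% |
| 2 | 0.92% | 1.4% | 10.6% | 42% |

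**What an interval would say.** For 5/375 v 0/125 the Newcombe 95% interval for the difference is −1.7 to +3.1 percentage points: an excess of up to about 3 points is not excluded. For 0/375 the exact upper limit is 1 − 0.025^(1/375) = 0.98% over 168 days, or about 2.1 per 100 person-years.

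**The case against.** **The feared reading is not written down.** A reader might infer that the plan will call five infections in vaccinees and none on placebo a finding of no difference. No section says so. Section 9.5.3.2 says only that incidence will be compared. Section 9.7.5.1 calls the safety analysis mainly descriptive, makes the chi-square test optional and speaks of adverse reactions without naming HIV. The 0.05 sentence sets a threshold, not an interpretation. All of this stands: the misreading is a foreseeable risk, not a stated rule.

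**Twelve is not a general minimum.** It applies to both doses pooled and to an excess in vaccinees. The singular wording of 9.5.3.2 favours pooling but does not fix it; by dose the minima are nine and six, and three infections suffice if all are on placebo. This also stands. The last figure does not help the plan, though: the rule signals apparent protection far more readily than harm.

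**Participants are not protected by this test.** A reader might infer that low power disables the safety rules. It does not. Pausing at one infection and possible termination at five are counts over all arms and use no P value. Section 9.7.6 gives the DSMB other HIV thresholds (above 2.5% and above 5%), which do not match those in 7.5. That mismatch is a separate matter, and the two sections must be reconciled.

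**Low power for a rare secondary endpoint is ordinary, and detail belongs in the SAP.** Both are true. The protocol claims no HIV power, and it refers to an SAP that was not available for this review. The missing interval is therefore not itself the fault. The point is that the protocol commits to a comparison and names for it only a method that can hardly answer the question. Nor is the result wholly predetermined: a five-fold rise at 2 per 100 person-years would be detected 42% of the time.

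**Conclusion.** The point holds in limited form. For pooled vaccine against placebo, an excess of HIV infections in vaccinees cannot reach two-sided P≤0.05 by Fisher's test with fewer than 12 infections, more than twice the count of five in section 7.5. Moderate harm would almost always be missed: power for a doubling is at most 1.4% over the assumed background range of 0.2 to 2 per 100 person-years. A non-significant result would be weak evidence on the risk that section 12.3.1 names.

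This rests on full arms of 375 and 125, on reading the 0.05 sentence as covering safety tests, and on assumed background rates. The minimum of 12 needs no background rate and is unchanged by 15% loss. The documents do not support the stronger claims that the plan would declare no difference or that its stopping counts are impaired. It is a worthwhile wording change to how the comparison is reported, not a flaw in the trial's conduct.

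**What to change.** In section 9.5.3.2, replace the bare commitment to compare the groups with wording such as: HIV incidence in vaccinees (pooled, and by dose) and in placebo recipients will be reported with exact 95% confidence intervals, together with a 95% confidence interval, by a named method, for the vaccine-minus-placebo difference; the conclusion will state the largest excess risk that the upper limit does not exclude; a P value above 0.05 will not be taken as evidence of no increase in risk.

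The SAP should carry the same text. The cost is a few lines and one small table; no dose, schedule, stopping rule or sample size changes. The downside is a less reassuring safety statement, because with these numbers the upper limit will probably leave a material excess open.
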